## STUDY SUMMARY

[figure not shown]
Study Title	Quality of life after cardiac surgery
Internal ref. no. (or short title)	QUACS
Study Design	Observational
Study Participants	8004
Follow up duration (if applicable)	1 year
Planned Study Period	3 years

**STUDY FLOW CHART**

## 1 BACKGROUND

Every year, around 40 000 patients undergo open heart surgery in the UK. During the last twenty years heart surgery has become much safer. As a result, the number of patients having heart surgery has steadily increased, and more frail and elderly patients are being offered increasingly complex open heart surgery for various heart problems.

For most patients, heart operations improve both survival and quality of life (QoL). Unfortunately, this is not true for all. In a small percentage of patients, a heart operation can abruptly shorten life, and in some patients, QoL may be adversely affected in the long term. When dealing with the important outcome of survival, we can measure the risk to life from having a heart operation and the risk to life from not having one quite precisely in most heart conditions and for most patients. However, we have very little idea about the impact of heart operations on QoL for individual patients, which is the outcome that many patients care about most of all.

At present, we are unable to provide patients with robust information on how an operation will affect their QoL. This research project will provide this information, so that patients are able to give evidence-based informed consent when they are contemplating a major heart operation.

Heart operations that improve neither survival nor QoL are harmful to patients and a drain on NHS resources. This study seeks to identify them with a view both to improve decision making by patients and doctors and to help eliminate ill-advised resource use in the NHS.

## 2 RATIONALE

In cardiac surgery, as in all branches of medicine, we treat patients so as to achieve two objectives:

[figure not shown]
- to improve quality of life (QoL)
- to improve survival

Deciding on an operation to improve survival is now easier due to sophisticated tools (EuroSCORE II & Tute) that measure and compare the risk to life of an operation with the risk to life from not having an operation. No such tool exists for QoL which is often the most important outcome for the patients.

Although some studies of cardiac surgery have included QoL as an outcome measure, no study has ever analysed the changes in QoL over time in the postoperative period and no study has ever analysed the relationship between individual patient and operation characteristics and the QoL outcome.

We know that most patients having heart surgery have symptoms (such as pain and breathlessness) which affect their QoL, and they submit to surgery in the hope of achieving relief from these symptoms and thus improving their QoL. We also know that, immediately after surgery, QoL is actually worse for all patients because postoperative pain, hospitalisation and functional limitation all have an impact. The normal scenario thereafter is that QoL then begins to improve, reaches the level it was before the operation and then hopefully exceeds it so that there will come a time when any QoL lost through surgery is 'paid back' by QoL gained. From that point onwards, the patient truly begins to benefit from having had the operation. The changes in QoL as a consequence of a typical major heart operation over time are graphically illustrated in the figure.

impact of a successful major open heart operation on quality of life

This is true for most patients, but not for all. A few will die from the operation. Some never regain the preoperative level of QoL, and some may not achieve a subsequent QoL improvement that matches or exceeds the QoL loss that occurs after the operation. Previous work indicates that between 8-19% of patients will experience a fall in QoL that does not recover.

When patients consent to major intervention, such as cardiac surgery, they need to know two things:

- 1) the risk to life of having an operation compared with the risk of not having an operation
- 2) the impact of an operation on QoL compared with the impact of not having an operation

Currently, we are able to provide detailed individualised information on the first so that we can identify those patients likely to benefit in terms of survival. We do not have such individualised information for QoL. We know that, overall, there is a net benefit in QoL after heart surgery, but we also know that in a sizeable minority of patients, QoL may not improve and may actually worsen after heart surgery, yet we do not have the tools that allow us to identify the patients who will lose in QoL terms. This study will address this knowledge gap.

We shall use existing tools to measure QoL in patients having major heart surgery. QoL will be measured before the operation and monthly afterwards for 12 months in order to answer the following questions:

- 1) How does having heart surgery affect the QoL immediately after the operation?
- 2) How long does it take patients to return to the same QoL they had before the surgery, if they ever do?
- 3) How long does it take patients to regain any loss of QoL due to the operation? Does QoL improve thereafter? And to what extent?
  - a) In other words will surgery 'add value' to their QoL?
  - b) If so, when?
- 4) What proportion of patients will achieve a net benefit in QoL?
- 5) Are there features that can predict who will benefit in terms of QoL and who will not?

Based on the above findings we intend to create a risk model to predict the following:

- 1) who will experience QoL net improvement and who will not within 12 month of surgery.
- 2) what is the net gain/loss of QoL that an operation may produce, and for which patients?
- 3) how long before a patient having a heart operation begins to benefit in terms of QoL

We will use the data to develop an electronic calculator to enable quick and robust evaluation of the impact of heart surgery on the QoL of individual patients. The calculator will be tested by patients and their feedback will be used to refine it so that the final version made available in the clinical setting will function in an accessible, user-friendly and understandable way. Patients will then be in a position to decide if they wish to proceed to surgery based on a full knowledge of *both* surgical risk and the potential impact on QoL.

When completed, the study will:

- 1) improve the process of informed consent by patients
- 2) improve the process of medical decision making by doctors
- 3) as a result of 1 and 2 above, reduce the harm done to patients by unnecessary or ill-advised operations and estimate the cost of such operations to the NHS

- 4) pioneer a model by which other specialties can measure their own QoL outcomes

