### **3 RESEARCH QUESTION/AIM(S)**

- 1) who will experience QoL net improvement and who will not within 12 month of surgery
- 2) what is the net gain/loss of QoL that an operation may produce and for which patients
- 3) how long before a patient having a heart operation begins to benefit in terms of QoL

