#### **3.1 Objectives**

From answering the above questions we will be able to :

- 1) improve the process of informed consent by patients
- 2) improve the process of medical decision making by doctors
- 3) as a result of 1 and 2 above, reduce the harm done to patients by unnecessary or ill-advised operations and estimate the cost of such operations to the NHS

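### The protocol promises to identify and cost unnecessary operations and to state the QoL an operation produces, but change from baseline in operated patients alone cannot support those claims

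*Protocol*

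**What the plan says.** **What is promised.** Section 1 refers to operations that improve neither survival nor QoL and continues: "This study seeks to identify them with a view both to improve decision making by patients and doctors". Section 2 lists among the results of the completed study that it will "reduce the harm done to patients by unnecessary or ill-advised operations and estimate the cost of such operations to the NHS", and Section 3.1 repeats this as objective 3. Aim 2 in Section 3 asks "what is the net gain/loss of QoL that an operation may produce and for which patients". The calculator described in Section 2 is to give a "robust evaluation of the impact of heart surgery on the QoL of individual patients", and patients are then to decide on that basis whether to proceed.

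**The context.** Section 2 gives the QoL information needed at consent as "the impact of an operation on QoL compared with the impact of not having an operation". It says that individualised QoL information is lacking and adds "This study will address this knowledge gap".

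**What is measured.** Section 2: "We shall use existing tools to measure QoL in patients having major heart surgery". Sections 4.1 and 4.3 confine the cohort to patients undergoing cardiac surgery. Section 6.1 schedules QoL at baseline, at discharge and monthly to 12 months. In Section 5.5 the three primary outcomes are (1) the difference in QoL between baseline and follow-up, (2) whether QoL has returned to its baseline level, and (3) whether the gains over baseline exceed the losses when summed over follow-up. The three SF12 outcomes use the same definitions. The risk model is built on outcome (3).

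**The concern.** Pre-operative QoL is what the patient had before surgery. It is not what the patient would have had over the next 12 months without surgery. Section 2 says that most of these patients have symptoms before the operation. Untreated disease could worsen over the year, or patients listed at a low point could drift upwards. A patient who ends below baseline may still be better off than without the operation, and one who ends above baseline might have improved anyway.

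If change from baseline is read as the effect of surgery, two things go wrong. Operations could be counted, and their cost added up, as ill-advised when the data cannot show this. The calculator could also present a predicted before-after change as what surgery does, at the moment when the patient is choosing between surgery and no surgery. The error can go in either direction.

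**Working it through.** **1. The protocol's own figure.** Section 5.1 gives a minimum of 6670 patients for a sensitivity of 0.75 ± 0.03 at 95% confidence, with 12% not regaining QoL.

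- N = z² × Se × (1 − Se) / (d² × p) = 3.8415 × 0.75 × 0.25 / (0.03² × 0.12) = 6669.2, rounded up to 6670. This reproduces.
- 6670 × 1.2 = 8004. This reproduces the stated total.
- The half-widths 1.96 × √[p(1 − p)/6670] are 0.65% at p = 8% and 0.78% at p = 12%, matching the stated 0.7% and 0.8%.

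The inputs are a sensitivity, a precision and a rate of not regaining QoL. None refers to QoL without an operation, so the study is sized for prediction and estimation among operated patients.

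**2. What outcome (3) measures.** For one patient, let B be pre-operative QoL, Y₁(t) QoL after surgery, and Y₀(t) the QoL the patient would have had at the same time without surgery.

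- Observed change: D(t) = Y₁(t) − B
- Untreated change: U(t) = Y₀(t) − B
- Effect of surgery: E(t) = Y₁(t) − Y₀(t) = D(t) − U(t)

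Outcome (3) depends on whether ΣD(t) is positive. Whether surgery improved QoL over the period depends on ΣE(t) = ΣD(t) − ΣU(t). The two sums are equal only if ΣU(t) = 0, as it is when untreated QoL stays flat. The study observes D(t) and never observes U(t).

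**3. Illustration.** The values below are assumptions, not protocol figures. They show two hypothetical patients, with an average change over follow-up of −0.05 and +0.05 utility.

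| Assumed average untreated change U | Effect if D = −0.05 | Effect if D = +0.05 |
|---|---|---|
| −0.10 | +0.05 | +0.15 |
| −0.05 | 0 | +0.10 |
| 0 | −0.05 | +0.05 |
| +0.05 | −0.10 | 0 |
| +0.10 | −0.15 | −0.05 |

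Each entry is D − U. The first patient fails outcome (3) and the second meets it in every row, yet the sign of the effect changes down both columns. The study data fit all five rows equally well.

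**4. Whether the protocol fills the gap by other means.** It describes no unoperated, deferred or waiting-list group, no external natural-history source and no modelled untreated course. It states no limit on causal interpretation. For survival, Section 2 relies on existing tools that compare operating with not operating, and says that no such tool exists for QoL. All six outcomes in Section 5.5 are QoL outcomes, so the survival half of the Section 1 definition is not assessed by them either.

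**The case against.** The best defence is that this is a prediction study and largely describes itself as one. Section 2 plans measurement before the operation and monthly afterwards, and one of its questions is how long patients take to return to their previous QoL. Aims 1 and 3, read as recovery relative to baseline, can be answered by this design. All of that stands.

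Three further points also stand, and they limit what can be said.

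- A reader might infer from Section 2 that the study undertakes to estimate QoL without an operation. The protocol never says so outright. The comparison with not operating is given as what patients need, and the gap that the study will address follows most directly on the lack of tools to identify who will lose QoL after surgery.
- A reader might infer that every patient without positive net benefit is to be classed as having had an ill-advised operation. Section 5.5 attaches no such label, and Section 1 requires no gain in survival as well as none in QoL.
- The wording of the calculator is still open. Sections 2 and 11 provide for patient testing, and Section 11 for external validation.

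It can also be said that Section 3.1 presents harm reduction as a consequence of better consent and decision making, not as a quantity to be estimated. That is fair for harm reduction. It does not cover the cost estimate, which requires deciding which operations were unnecessary, nor the Section 1 undertaking to identify them. External validation does not close the gap either: checking predictions against the observed course of operated patients tests the prediction, not the effect of surgery.

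**Conclusion.** The point holds for specific claims: identifying operations without benefit (Section 1), costing unnecessary or ill-advised ones (Sections 2 and 3.1), and describing the calculator's result and aim 2 as the impact or product of the operation (Sections 2 and 3). These need the course without surgery, or an assumption about it, and the protocol supplies neither. They would follow from change from baseline only if untreated QoL stayed flat for 12 months; the survival condition in Section 1 would still have to be settled separately.

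It does not follow that the study is invalid. Predicting QoL after surgery relative to pre-operative QoL is well defined, and the sample size, data collection and analyses in Section 5.5 are unaffected. Nor can a percentage of wrongly classified patients be quoted. A reader may want one, but it would rest entirely on an untreated course that the protocol does not give, and even its direction is unknown.

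This is a matter for the protocol itself: objectives, population and reference point are fixed there, and no later analysis plan can recover the missing comparison without outside assumptions.

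**What to change.** In Sections 1, 2, 3 and 3.1 and in the calculator output, restate the quantity as *predicted change from pre-operative QoL within 12 months among patients who have surgery*. Withdraw the claims to identify and cost unnecessary or ill-advised operations, or make them explicitly conditional on a stated assumption about the untreated course and its source.

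Optionally, report how many outcome (3) classifications would change under assumed untreated courses in both directions, for example −0.10, −0.05, 0, +0.05 and +0.10 utility, each labelled as an assumption. Running only declines would favour surgery by construction.

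The cost is a narrower stated claim, some redrafting and, if the optional analysis is done, a little more work on data already collected. No control group and no extra data are needed.

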### **3 RESEARCH QUESTION/AIM(S)**

- 1) who will experience QoL net improvement and who will not within 12 month of surgery
- 2) what is the net gain/loss of QoL that an operation may produce and for which patients
- 3) how long before a patient having a heart operation begins to benefit in terms of QoL

#### **3.1 Objectives**

From answering the above questions we will be able to :

- 1) improve the process of informed consent by patients
- 2) improve the process of medical decision making by doctors
- 3) as a result of 1 and 2 above, reduce the harm done to patients by unnecessary or ill-advised operations and estimate the cost of such operations to the NHS

### **4 Investigational Plan**

#### **4.1 Design**

- 1) The proposed study will be a multi- centres prospective observational study to assess in patients with a EuroSCORE II of 3 or greater undergoing cardiac surgery who will experience QoL net improvement and who will not within 12 month of surgery.

#### **4.2 Setting and Investigators**

Nationally all acute NHS cardiac surgical centres will be invited to participate in this study with Royal Papworth as the lead centre.

#### **4.3 Study Population**

Eligible patients will be elective cardiac surgery patients with a EuroSCORE II of 3 or more undergoing cardiac surgery.

#### **Inclusion criteria**

EuroSCORE II  $\geq$  3% or EuroSCORE logistic of  $\geq$  6%

Patients undergoing routine/ urgent cardiac surgery

Patients must have the ability to provide informed consent

#### **Exclusion criteria**

Patients undergoing salvage or emergency operations.

Patients having transcatheter aortic valve implantation or TAVI

## 5. RECRUITMENT AND SAMPLING

### 5.1 Sampling

The study will recruit a total of 8004 patients over two years and follow them up for 12 months. This sample size was derived as follows: according to Abah et al the percentage of people expected not to regain QoL after heart surgery and after 12 months is between 8-19%. Additionally, there is a 4% predicted mortality rate for heart surgery in the UK in the higher risk population which is the subject of this study. Therefore, a conservative estimate is that 12% of patients in this study would not regain QoL. Assuming the 12% rate as a reference value, with a minimum of 6670 patients we would be powered to produce a predictor tool with a sensitivity of at least 0.75 (or true positive rate to identify those patients that do not regain QoL after surgery) and a 3% error ( $0.75 \pm 0.03$ ) at the 95% confidence level. Anticipating a non-response rate of 20%, we will recruit an additional 1334 patients to compensate for this, giving a total of 8004. Based on the above, the study will estimate the proportion of patients who do not regain QoL after 12 months with a 95% confidence of  $\pm 0.7\%$  (for a rate of 8%) and  $\pm 0.8\%$  (for a rate of 12%) with 6670 patients.

Recruitment and drop-out rates will be continuously monitored by the trial steering committee (TSC). To recruit 8004 patients, we plan to approach all 36 cardiac centres in the UK. Assuming only 30 centres take part (a feasible number based on our NIHR ETTAA study) and a two-year recruitment period, there will be 20000 patients with a EuroSCORE II  $\geq 3$  who would be eligible for the study over two years. Our sample size calculation requires that 40% of the eligible patients consent over the two-year period. This translates into no more than 134 patients per centre per year, a recruitment target that is conservatively achievable. Based on our original approach to 5 centres, the recruitment rate will average 192 patients per centre per year, so that the required 134 patients per centre per year is achievable and will be carefully monitored by the project management team and the TSC as described in the section 9.4 of this protocol.

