## 11. PATIENT & PUBLIC INVOLVEMENT

Patients and the public are represented by lay members of the Trial Steering Committee. Both the electronic and paper versions of data collection are currently being tested by our patient research ambassadors who will help refine the method to ensure it is user-friendly.

As a preliminary exploration, we approached a series of patients attending cardiac surgical clinics to consider surgery for their cardiac condition. They were shown the TUTE calculator (which predicts their likely benefit in terms of survival) and were asked if they would consider a similar tool predicting QoL outcomes useful to them. The response was invariably positive.

Throughout the course of the study we shall hold yearly patient events to discuss the construction of the QoL prediction tool and in particular the way patients would want this information presented to them so it will be understandable and of value. During the patient events we shall also ask previous cardiac patients what information they would have found useful in aiding them to make the decision to undergo surgery. This development will help design the end product that would be made available to patients and doctors.

Once data collection is completed, a descriptive report will outline the pattern of QoL loss and gain over time after cardiac surgery. The data will then be analysed by logistic regression to identify the factors predictive of loss and gain in QoL outcomes. A full analysis of factor interactions will be carried out. The data will be divided into a development dataset and a validation dataset. The development dataset will then be used to construct a number of risk models to predict the extent and likelihood of any QoL benefit or loss from cardiac surgery. All the models will then be tested for calibration and discrimination against the validation dataset to identify the most useful and robust model. The chosen model will then be developed into a QoL outcome calculator (QoLculator) which will be offered for testing and external validation, following which the calculator will be made available on-line and as a mobile phone app for patients and doctors.

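### The sample-size paragraph presents a precision calculation as power to achieve a sensitivity of at least 0.75

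*Protocol*

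**What the plan says.** Protocol section 5.1 (Sampling) takes as its planning value that "a conservative estimate is that 12% of patients in this study would not regain QoL". It then states that, "with a minimum of 6670 patients", "we would be powered to produce a predictor tool with a sensitivity of at least 0.75". The sentence goes on to give a 3% error, written as 0.75 ± 0.03, "at the 95% confidence level". Sensitivity is defined there as the true positive rate for patients who do not regain QoL. No power value is given, nor a sensitivity that the study aims to exclude.

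Model evaluation is described in section 11 (Patient & Public Involvement). The data are to be divided into a development and a validation dataset, and the candidate models are to be "tested for calibration and discrimination against the validation dataset". The split fractions are not given. External validation of the resulting calculator is to follow.

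**The concern.** The claim in section 5.1 is about what the study will produce: a tool whose sensitivity is 0.75 or better. The number of patients does not determine how well a prediction model works. That depends on how strongly the predictors relate to the outcome and on where the cut-off is placed. The number of patients determines how closely the tool's performance can be measured.

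The calculator is meant to inform patients who are deciding on surgery, and this sentence is the main justification for recruiting 8004 people. A funder, ethics committee or steering committee could take from it that a sensitivity of 0.75 is secured by design. The calculation promises only that, if sensitivity turns out near 0.75, the estimate will be reasonably tight.

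**Working it through.** **Inputs, all from section 5.1:** proportion not regaining QoL 0.12; sensitivity 0.75; half-width 0.03; confidence level 95% (z = 1.96); minimum number 6670.

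**1. Reproducing the protocol's figure.** The single-proportion precision formula, divided by the proportion who do not regain QoL, is

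N = z² × Se × (1 − Se) / (d² × prevalence)

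- Cases needed: 1.96² × 0.75 × 0.25 / 0.03² = 800.3
- Patients needed: 800.3 / 0.12 = 6669.4, rounded up to 6670

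This matches exactly and so identifies the method. Every term describes the precision of an estimate. None is a power, a null value or a cut-off.

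**2. What 6670 patients deliver.** Expected patients not regaining QoL: 6670 × 0.12 = 800.4. Half-width at a sensitivity of 0.75: 1.96 × √(0.75 × 0.25 / 800.4) = 0.030. The 95% interval is therefore about 0.72 to 0.78, and its lower limit lies below 0.75.

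**3. Does the number secure 0.75?** With 800 cases and a true sensitivity of exactly 0.75, the binomial probability of observing 0.75 or more (at least 600 of 800) is 0.519. The probability of observing less is 1 − 0.519 = 0.481, about half. If true sensitivity is 0.72, the observed value reaches 0.75 in about 3% of studies.

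**4. Does precision depend on the tool being good?** Hardly. Half-width with 800 cases:

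| True sensitivity | 95% half-width |
|---|---|
| 0.60 | 0.034 |
| 0.70 | 0.032 |
| 0.75 | 0.030 |
| 0.80 | 0.028 |

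A weaker tool would be measured almost as precisely as a good one, so the sample size cannot be what makes the tool good. The table also shows that for any sensitivity of 0.75 or more the half-width is at most 0.03.

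**5. Why the cut-off matters to the wording.** Sensitivity belongs to a model at a particular cut-off. A rule that flags 75% of patients at random has sensitivity 0.75. Its positive predictive value is 0.75 × 0.12 / (0.75 × 0.12 + 0.75 × 0.88) = 0.12, the base rate. A sensitivity of 0.75 is therefore meaningful only at a stated cut-off and alongside other measures.

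**6. Which patients the ±0.03 applies to.** It uses all 800 expected cases, whereas section 11 divides the data. If half the cases were in the validation set (an assumption), 400 cases would give about ±0.042. With 30% (also an assumption), 240 cases would give about ±0.055. The restated sentence should therefore name the number of cases on which it depends.

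**The case against.** The strongest reply is that nothing has been miscalculated and the precision meaning is already on the page. The same sentence gives 0.75 ± 0.03, and the paragraph ends with another statement of precision, for the proportion not regaining QoL. This stands: 6670 is right for what it computes, and a careful reader can recover the correct meaning. It does not rescue the main clause, which still says the study is powered to produce a tool of that quality.

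A second reply is that the words *at least* are defensible. Above 0.5 the half-width shrinks as sensitivity rises, so 0.03 is an upper bound on the error for any sensitivity of 0.75 or more. This also stands, and the rewording should keep that information. As a planning bound the phrase is sound; as a floor on the tool's performance it is not.

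Some stronger readings are tempting, but the documents do not support them.

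- *The study could declare success by moving the cut-off.* The protocol nowhere makes 0.75 a success criterion; it appears once, as a sample-size input. Models are chosen on calibration and discrimination in a validation dataset.
- *The plan never shows that the tool separates patients who lose QoL from those who do not.* Discrimination is that property, and section 11 plans to test it.
- *The protocol lacks a specificity, a cut-off and reporting rules.* These commonly belong in the statistical analysis plan, which section 5.5 mentions and which is not at hand.
- *True sensitivity must be well above 0.75 for the lower confidence limit to clear 0.75.* This is true arithmetically, but it tests a threshold that the protocol does not set.

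**Conclusion.** The point holds as a misstatement of what the sample size delivers. The calculation supports a conditional statement: if the tool's sensitivity is 0.75, about 800 patients who do not regain QoL will estimate it with a 95% confidence interval of about 0.72 to 0.78. It does not support power to reach 0.75; a tool with exactly that sensitivity would be observed below it in about 48% of such studies.

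This rests on the protocol's own 12% and on all 800 cases contributing to the estimate. A reader might infer that 6670 is wrong or that model evaluation is inadequate. Neither follows: the number reproduces exactly, and validation of calibration and discrimination is planned. The defect lies in the claim, not in the design.

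**What to change.** In section 5.1, replace "we would be powered to produce a predictor tool with a sensitivity of at least 0.75" with wording such as: *we would be able to estimate the tool's sensitivity, if it is 0.75 or more, to within ±0.03 (95% CI 0.72 to 0.78 at 0.75) when about 800 patients who do not regain QoL are available for that estimate*. Keep the definition of sensitivity, and drop the separate mention of the 3% error, which the new wording contains.

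Add one sentence saying that this is the precision at a given cut-off, not a guaranteed or stand-alone performance target. A cross-reference to the calibration and discrimination testing in section 11 would show where the tool's performance is judged.

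The cost is wording only. The sample size, design and analysis do not change; the stated claim becomes slightly less favourable.

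### The 20% non-response allowance was calculated on 6670 rather than on the number recruited, so 8004 recruits leave about 6403 responders, below the plan's own minimum of 6670.

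*Protocol*

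**What the plan says.** Section 5.1 bases the sample size on the precision of a predictive tool. It takes 12% as the proportion of patients who do not regain quality of life, and states that "with a minimum of 6670 patients we would be powered to produce a predictor tool with a sensitivity of at least 0.75", with an error of 3 percentage points, "at the 95% confidence level". It then makes the allowance for loss: "Anticipating a non-response rate of 20%, we will recruit an additional 1334 patients to compensate for this, giving a total of 8004". The precision it quotes for the proportion not regaining quality of life (±0.7% at a rate of 8%, ±0.8% at 12%) is also given for 6670 patients.

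The total of 8004 is carried into the Study Summary ("Study Participants 8004") and is the basis in section 5.1 for two recruitment figures: 40% consent among 20000 eligible patients, and at most 134 patients per centre per year across 30 centres over two years.

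**The concern.** The extra 1334 patients are 20% of the number needed at the end, not 20% of the number recruited. A non-response rate is ordinarily a share of those enrolled, so the required number should be divided by 0.8, not multiplied by 1.2. If so, the plan sets a minimum and a loss rate and then gives a recruitment target that misses the minimum at that rate.

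At stake are the headline sample size, the two recruitment figures derived from it, and the loss the study believes it can absorb. That last point has practical weight: section 6.3 asks patients for monthly questionnaires on their own devices or on paper, and section 5.1 has the steering committee monitor drop-out. A tolerance believed to be 20% would really be 16.7%.

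**Working it through.** **Inputs, all from section 5.1:** sensitivity 0.75; half-width 0.03; 95% confidence (z = 1.96); rate of not regaining quality of life 12%; minimum 6670; non-response 20%; addition 1334; total 8004; 30 centres, two years, 20000 eligible patients.

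**1. The base number reproduces.**

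N = z² × Se × (1 − Se) / (d² × rate) = 1.96² × 0.75 × 0.25 / (0.03² × 0.12) = 6669.4, rounded up to 6670. This corresponds to about 800 patients who do not regain quality of life (6670 × 0.12). The formula counts patients whose outcome is observed, so 6670 is the number that must remain after non-response.

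**2. How the plan reached 8004.**

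1334 / 6670 = 20.0%, and 6670 × 1.2 = 8004, exactly the stated total.

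**3. What 8004 delivers at 20% non-response.**

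8004 × 0.8 = 6403.2, so about 6403 responders. The shortfall is 6670 − 6403 = 267, or 4.0% of 6670.

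**4. What is needed to keep 6670.**

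6670 / 0.8 = 8337.5, so 8338 recruits. That is 8338 − 8004 = 334 more than planned (1668 added instead of 1334).

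**5. The loss that 8004 does cover.**

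1334 / 8004 = 16.7%.

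**6. Effect on precision and recruitment.** The half-width for sensitivity is 1.96 × √(0.1875 / (n × 0.12)), where 0.1875 = 0.75 × 0.25. For a proportion p it is 1.96 × √(p(1 − p) / n).

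| Quantity | At 6670 | At 6403 |
|---|---|---|
| Expected patients not regaining quality of life | 800 | 768 |
| Half-width, sensitivity | 3.00 points | 3.06 points |
| Half-width, proportion at 8% | 0.65% | 0.66% |
| Half-width, proportion at 12% | 0.78% | 0.80% |

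| Recruitment figure | Total 8004 | Total 8338 |
|---|---|---|
| Per centre per year (total / 60) | 133.4 | 139.0 |
| Share of 20000 eligible | 40.0% | 41.7% |

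**The case against.** The strongest reply is that the slip changes very little. The precision statements are tied to 6670, not to 8004. At 6403 the half-widths for the proportion still round to the printed 0.7% and 0.8%, and the sensitivity half-width of 0.0306 still rounds to 0.03. Recruiting 139 per centre per year is well inside the average of 192 that the protocol expects from its approach to five centres. The inputs are also approximate: at a rate of 13% instead of 12%, the required number falls to 800.3 / 0.13 = 6157, below 6403. All of this stands, and it limits the importance of the point.

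A second reply is that the 12% seems to combine 8% not regaining quality of life with 4% mortality, and that a death is not a missing questionnaire. Suppose deaths are known in full and the 20% applies only to survivors, which the protocol does not state. Then 8004 recruits give 320 deaths plus 492 to 512 surviving non-regainers who respond (8% of survivors or 8% of all recruits, times 0.8). That is 812 to 832 events and a half-width of 2.98 to 2.94 points, within the target. Patients with a known outcome would number 320 + 0.8 × 7684 = 6467, still below 6670. So the 3.06-point figure assumes that non-response falls equally on patients who die, but the missed minimum does not depend on that assumption.

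Two other readings could rescue 8004, and neither fits the text. The 20% could be a share of the 6670 final responders, but that is not the usual meaning and the protocol does not define it so. It could be refusal of consent, but section 5.1 handles consent separately and computes the 40% share from 8004, which makes 8004 the consented number.

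**Conclusion.** The allowance is wrong as written. With 20% non-response among recruits, 8004 yields about 6403 analysable patients, 267 (4.0%) short of the stated minimum. Keeping the minimum takes 8338 recruits, and the present total covers only 16.7% loss. This rests on the ordinary meaning of a non-response rate, as a share of those recruited, and on 6670 being the number with an observed outcome, as the reproduced formula requires.

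The consequence is modest: 0.06 percentage points on the sensitivity half-width if non-response is unrelated to outcome, and no change to the printed precision of the proportion. The study's validity is not threatened. The correction is still worth making, because the stated target does not do what the protocol says it does and it feeds the recruitment figures.

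**What to change.** Either of two corrections to section 5.1 resolves it.

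- **Keep 8004 and restate what it gives.** Say that it allows for 16.7% non-response, or that at 20% non-response it gives about 6403 analysed patients and a half-width of ±3.1 points for a sensitivity of 0.75. The Study Summary, the centre rate and the consent share stay as they are. The cost is wording only.
- **Keep 6670 and 20% non-response.** Change the total to 8338 here and in the Study Summary, the addition to 1668, the centre rate to 139 per year and the consent share to 41.7%. The cost is 334 more recruits, at a centre rate still below the 192 the protocol expects.

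The first is the lighter change and loses almost nothing. In either case, one sentence should say that the non-response rate is a share of recruited patients and whether deaths count as non-response or as observed outcomes.
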